IRB	Institutional Review Board
IP	Investigational Product aka Test Product
ISGA	Investigators static global assessment
Microbiome	Microorganisms in a particular environment
PHI	Protected Health Information
RNA	Ribonucleic Acid
SAE	Serious Adverse Event
Sponsor	DermBiont

SYNOPSIS

NAME OF SPONSOR: DermBiont Inc.	
NAME OF FINISHED PRODUCT: DBI-001	
NAME OF ACTIVE INGREDIENT(S): [REDACTED]	
Title of Study	Open label, single-dose, dose escalating evaluation of the safety and tolerability of three dose levels of DBI-001 in patients with Tinea pedis.
Investigator(s)	[REDACTED]
Study centre(s)	Santo Domingo, DR
Publication	N/A
Phase of development	Phase 2A
Objectives	
Primary Objective:
 
Evaluate the safety and tolerability of DBI-001 in patients with Tinea pedis.
 
Secondary Objectives:
 
• Evaluation of presence or persistence of [REDACTED] of DBI-001 following a single application of DBI-001• Effect of a single application of DBI-001 on the abundance of T. rubrum• Effect of a single application of DBI-001 on the signs and symptoms of interdigital T. pedis.
Study Design and Evaluation Methods	
A single-center, open label, dose escalating design will be used in a population of patients with interdigital Tinea pedis. The test product will be applied by study personnel at the investigational site. Each subject will have a single application of approximately 0.5 ml of the test article applied to each foot. Both affected and unaffected feet will be treated covering the web spaces, toes, toe nails as well as the plantar and lateral aspect of both feet.
 
Each of the three groups will have 4 subjects. After the first cohort has completed their day 7 visits, if no significant tolerability or safety issues identified the second cohort will be enrolled. After the second cohort has completed the day 7 visits and if no significant tolerability or safety issues is identified the third cohort will be enrolled.

Methodology	Open label, dose escalating
Number of patients	N=12 (3 cohorts) 4 patients per treatment group
Inclusion Criteria	
Subjects must meet all of the following criteria to be included in the study:
 
1. Witnessed, signed informed consent approved by Institutional Review Board/Independent Ethics Committee.2. A signed Health Information Portability and Accountability Act (HIPAA) authorization form which permits the use and disclosure of subject's individually identifiable health information.3. Male Subjects of any race 18 years of age and older.4. Subjects with a clinical diagnosis of interdigital T. pedis T. pedis interdigital defined as lesions localized to the interdigital spaces or predominantly interdigital, but may extend to other areas of the foot (the non-interdigital lesions should not be hyperkeratotic, i.e., characteristic of tinea pedis moccasin).5. Provisionally confirmed diagnosis at baseline by a positive potassium hydroxide (KOH) wet mount at the clinical site.6. The sum of the clinical signs and symptoms scores of the target lesion is at least 4 using the Grading and signs and symptoms of T. pedis detailed in section 6.6.1, including a minimum score of at least 2 for erythema AND a minimum score of 2 for either scaling/fissures or pruritus/burning (on a scale of 0-3, where 2 indicates moderate severity).

Exclusion Criteria	
Subjects with the following will be excluded from this study:
 
1. Any dermatological conditions that could interfere with clinical evaluations.2. Any underlying disease(s) or some other dermatological condition that requires the use of interfering topical or systemic therapy.3. Subjects that have not undergone the specified washout period(s) for the following topical preparations or subjects who require the concurrent use of any of the following topical medications applied to the foot: 

Topical astringents and abrasives (e.g. Burrow's solution)	1 week	

Topical antibiotics and antifungal on the affected area (e.g. Neomycin, Miconazole, Clotrimazole, Terbinafine)	2 weeks	

Anti-inflammatories, corticosteroids, topical immunomodulators (e.g. Pimecrolimus, Tacrolimus)	4 weeks	

 
4. Subjects that have not undergone the specified washout period(s) for the following systemic medications or subjects who require the concurrent use of any of the following systemic medications: 

Corticosteroids (including intramuscular injections) (e.g. Triamcinolone acetonide)	4 weeks	

Antibiotics (e.g. Tetracycline, Cephalosporins, etc.) and/or Antifungal agents (e.g. Fluconazole, Itraconazole, Terbinafine, etc.)	4 weeks	

Systemic immunomodulators (e.g. Cyclophosphamide, Azathioprine, Biologicals-Monoclonal Antibodies)	4 weeks	

 
5. Treatment of any type of cancer within the last 6 months.6. History of any significant internal disease (which contraindicates use of live microbiome e.g. leukemia, liver failure, cardiovascular disease)	Topical astringents and abrasives (e.g. Burrow's solution)	1 week	Topical antibiotics and antifungal on the affected area (e.g. Neomycin, Miconazole, Clotrimazole, Terbinafine)	2 weeks	Anti-inflammatories, corticosteroids, topical immunomodulators (e.g. Pimecrolimus, Tacrolimus)	4 weeks	Corticosteroids (including intramuscular injections) (e.g. Triamcinolone acetonide)	4 weeks	Antibiotics (e.g. Tetracycline, Cephalosporins, etc.) and/or Antifungal agents (e.g. Fluconazole, Itraconazole, Terbinafine, etc.)	4 weeks	Systemic immunomodulators (e.g. Cyclophosphamide, Azathioprine, Biologicals-Monoclonal Antibodies)	4 weeks
Topical astringents and abrasives (e.g. Burrow's solution)	1 week												
Topical antibiotics and antifungal on the affected area (e.g. Neomycin, Miconazole, Clotrimazole, Terbinafine)	2 weeks												
Anti-inflammatories, corticosteroids, topical immunomodulators (e.g. Pimecrolimus, Tacrolimus)	4 weeks												
Corticosteroids (including intramuscular injections) (e.g. Triamcinolone acetonide)	4 weeks												
Antibiotics (e.g. Tetracycline, Cephalosporins, etc.) and/or Antifungal agents (e.g. Fluconazole, Itraconazole, Terbinafine, etc.)	4 weeks												
Systemic immunomodulators (e.g. Cyclophosphamide, Azathioprine, Biologicals-Monoclonal Antibodies)	4 weeks												

	
7. Subjects who are known to be allergic to any of the test product(s) or any components in the test product(s) or history of hypersensitivity or allergic reactions to any of the study preparations as described in the Investigator's Brochure.8. AIDS or AIDS related complex by medical history.9. Known or suspected immune suppressive medications or diseases.10. Diabetes mellitus Type I or II by medical history.11. Peripheral vascular disease based on medical history.12. Any subject not able to meet the study attendance requirements.13. Subjects who have participated in any other trial of an investigational drug or device within 30 days prior to enrollment or participation in a research study concurrent with this study.
Test product, dose and mode of administration	
The test product will be applied by study personnel at the investigational site. Each subject will have a single application of approximately 0.5 ml of the test article applied to both affected and unaffected feet covering the web spaces, toes, toe nails as well as the plantar and lateral aspect of both feet. The product is formulated in a low viscosity aqueous gel and approximately 0.5 ml will be applied to each foot. The three dose groups are:
 
Cohort 1 dose 10^6/ml CFUs of [REDACTED]
 
Cohort 2 dose 10^7/ml CFUs of [REDACTED]
 
Cohort 3 dose 10^8/ml CFUs of [REDACTED]

Duration of treatment	A single application will be applied and then patients will be followed for 28 days

Criteria for evaluation	
Evaluations will be made at Screening, Day 1 / Baseline prior to the application of the test article and then 1 hour after application and study days 2, 3+1, 7+/-1, 14+/-2 and 28+/-2.
 
Subjects will also be queried for adverse events starting after the informed consent is signed and all timepoints following application.
 
Primary:
 
• Signs and symptoms of irritation 
Secondary:
 
• Data listing showing duration of time over which DBI-001 can be detected by molecular diagnosis• Change in abundance of T. rubrum by molecular diagnosis• Changes in the signs and symptoms of T. pedis• Changes in the T. pedis ISGA• Frequency of conventional culture negative• Frequency of KOH negative
Statistical methods	Descriptive

Safety Results:	Dermal Safety and Tolerability: Tolerability will be evaluated through assessment of selected local signs and symptoms (pain / burning, pruritus, erythema, edema, and scabbing/ crusting). Any local skin reaction that requires use of a concomitant therapy or causing study drug interruption or discontinuation should be reported as an AE. The scales to be used for assessing local skin reactions follow
Adverse Events:	During the study, subjects will be assessed for the occurrence of new and ongoing AEs. Descriptions of AEs will include the dates of onset and resolution (if resolved), maximum severity, and seriousness, corrective treatment, outcome, and the Investigator's assessment of causality. AEs present at any visit will be followed to resolution (return to normal or to the baseline state) or until clinically stable as determined by the Investigator.

Efficacy Results:	
• Proportion of samples at each time point in which [REDACTED] can be detected by molecular diagnosis.• Proportion of samples at each time point in which T. rubrum can be detected by molecular diagnosis• Relative abundance of T. rubrum at each time point• Change in abundance of T. rubrum• Changes in the signs and symptoms of T. pedis• Changes in the T. pedis ISGA• Change from dermatophyte culture positive to culture negative• Change from KOH positive to KOH negative
--------------------------	--

1. INTRODUCTION

1.1 Background Information

DBI-001 is a live bacterial product containing [REDACTED] [REDACTED] This product is being developed as a topical probiotic for the treatment of fungal infections of the skin and nails. [REDACTED] is an aerobic Gram-negative bacterium commonly found in the soil, water, vegetables and grains from the human food chain, and on the skin of healthy humans. DBI-001 is a human derived commensal organism being employed as a topical probiotic. The strain of [REDACTED] in the DBI-001 product is a strain [REDACTED] that DermBiont isolated from the skin of a healthy young adult. Based on DNA sequencing this strain has no known virulence factors nor genes that would indicate antimicrobial resistance. In vitro the [REDACTED] strain has been shown to inhibit the growth of *T. rubrum*. The [REDACTED] strain is sensitive to commonly used antibiotics.

New strains of probiotics and their applicability for curing disease through topical application has been reviewed (Kerry et al 2018). The microbiome in health and disease was initially studied as it related to the microbiome of the gut. It is now well recognized that all human epithelial surfaces have a microbiome community that can contribute to health and diseases. There are distinct microbial communities in the gut, the skin, the respiratory tract, the oral cavity, and the genital urinary tract.

The use of topical live bacterial products to treat skin diseases is a new and rapidly advancing therapeutic approach. To date at least three live bacterial products have been studied in the clinic. An ammonia oxidizing bacterium has been used in Phase 2 trials to treat acne patients (<https://clinicaltrials.gov/ct2/show/NCT02832063>). A coagulase-negative *Staphylococcus* has been used to treat patients with atopic dermatitis (Williams and Gallo 2017). A strain of *P. acnes* has been used to treat acne patients.

(<https://www.clinicaltrials.gov/ct2/show/NCT03450369?term=Naked+Biome&rank=2>).

Application of [REDACTED] to the skin of amphibians has been shown to be able to treat and prevent the acquisition of a lethal cutaneous fungal infection (Brucker et al. 2008). [REDACTED] produces at least two anti-fungal compounds violacein and indole-3 carboxaldehyde.

In vitro [REDACTED] has been shown to inhibit the growth of *T. rubrum*, a dermatophytic fungus commonly associated with diseases of the skin and nails in humans.

There are a number of recognized skin diseases associated with a group of fungi called dermatophytes. These include various forms of *Tinea pedis* (athlete's foot), onychomycosis (toe nail fungus), *Tinea cruris* (jock itch) and *Tinea corporis* (ring worm). Traditionally these are

thought to be caused by an “infection” with a dermatophyte. The current thinking is that when the dermatophyte is present there is disease and when it is absent there is no disease.

There are numerous antifungal drugs both oral and topical that in vitro are very potent and effective in inhibiting or even killing fungi. Despite these potent drugs the complete clinical and mycologic response rate in most clinical trials is well under 50%, most about 30%. It is not uncommon to see subjects who do respond, even complete clinical responses will still have positive cultures or microscopic evidence by KOH examination demonstrating the presence of a dermatophyte. There are also subjects with all of the signs and symptoms of disease from whom a dermatophyte cannot be cultured.

The human epithelial surfaces of the skin, gut, genital tract, and respiratory tract are at the interface with the outside world. These areas have long been known to be inhabited by microorganisms previously referred to as “the normal flora” which for the most part was thought to neither contribute much to health or disease. But in recent years with the availability of DNA sequencing what had been called the normal flora is also called the microbiome. The DNA sequencing was needed to establish this because many of the organisms are either difficult or impossible to grow using routine culture techniques. It has become apparent that a normal microbiome can contribute to health while an abnormal microbiome can be associated with disease. An abnormal microbiome associated with disease is called a dysbiosis.

Recent studies have focused in large part on the bacterial component of the cutaneous microbiome and little is known about the fungal component, the mycobiome.

It is possible that the skin diseases of the foot associated with dermatophytes represent a dysbiosis rather than an “infection” in the traditional sense. It is known that using conventional culture techniques dermatophytes can be cultured from the feet of people with no signs or symptoms of skin disease. In addition, the diseases of the foot associated with dermatophytes are seen far more commonly in people who wear shoes than in people who are barefoot.

It is possible that dermatophytes are in fact part of the cutaneous microbiome in at least some individuals. As part of the community of organisms that make up the cutaneous microbiome of the foot dermatophyte are kept in balance by other organisms such as bacteria. However, wearing shoes especially in warm climates and/or by people with sweaty feet changes the “micro climate” tipping the environmental condition to favor the dermatophyte resulting in the Tinea pedis and onychomycosis.

Current antimicrobial treatments do nothing to correct a dysbiosis and may in fact contribute to the dysbiosis resulting in these conditions frequently being chronic recurrent.

This is analogous to the better known vulvar vaginal candidiasis associated with uses of systemic antibiotics. A normal healthy vagina has a mixture of yeast and bacterial that keep each other in balance. By taking an oral antibiotic that decreased the bacterial component thus favor the growth of yeast can result in vulvar vaginal candidiasis.

It is also possible that subjects with the clinical features of disease who are culture and/or KOH negative may not be actually be false negative, but their disease could be associated with organisms other than the traditional dermatophytes or dermatophytes that are difficult if not impossible to culture with routine mycology cultures. There is a substantial literature implicating molds, yeast, and other organisms in these cases. Using DNA sequencing may more accurately characterize the community of organisms associated with these condition that has been accomplished to date with routine dermatophyte culture and KOH examinations.

It is hoped that the topical probiotic DBI-001 will improve the treatment of common diseases of the skin and nails associated with dermatophytes. Assuming good safety and tolerability in this trial the sponsor will then enroll patients with *T. pedis* and onychomycosis into larger vehicle-controlled efficacy trials.

The purpose of the current protocol is to establish the safety and tolerability of a single application of [REDACTED] to the feet of patients with proven *T. pedis*. In addition, the effect of [REDACTED] on the *T. pedis* will also be evaluated.

1.2 Rationale

A single application of [REDACTED] to the skin of three different species of amphibians in two independent laboratories has been shown to treat and prevent a lethal cutaneous fungal infection. In-vitro [REDACTED] has been shown to significantly inhibit the growth of the fungus, *T. rubrum* most frequently associated with *T. pedis*. Based on these observations' topical application of the probiotic [REDACTED] could treat *T. pedis*. This protocol intends to enroll only males because *T. pedis* is far more common in men than women.

2. POTENTIAL RISKS AND BENEFITS

2.1 Potential Risks

Despite the fact that [REDACTED] is found in the cutaneous microbiome of some people as well as in the human food chain it is possible that application of [REDACTED] could result in a worsening of the *T. pedis*, impetigo, or cellulitis. A mild detergent solution will be used to collect samples and it could cause a local irritant reaction.

2.2 Potential Benefits

In amphibians a single application of [REDACTED] has been shown to treat their cutaneous infection. It is possible that a single application of [REDACTED] could result in improvement even a clinical and microbiologic cure of the subject's *T. pedis*. Upon subject's study completion, subjects who continue to have signs and symptoms of *T. pedis* will be given an approved topical anti-fungal agent with application instructions.

It should be noted that if worsening of the *T. pedis*, impetigo, or cellulitis were to occur, [REDACTED] is susceptible to commonly used topical and oral antimicrobials and antibiotics.

3. STUDY OBJECTIVES AND PURPOSE

The purpose of the study is to evaluate the safety and tolerability of DBI-001 in patients with *Tinea pedis*. Secondly to evaluate presence or persistence of [REDACTED] of DBI-001 following a single application of DBI-001. Thirdly to see the effect on the abundance of *T. rubrum*. Lastly to see the effect of a single application of DBI-001 on the signs and symptoms of interdigital *T. pedis*.

4. STUDY DESIGN AND ENDPOINTS

4.1 Description of the Study Design

A single center open label dose escalating study design will be used in a population of patients with interdigital *Tinea pedis*. Each subject will have a single application of approximately 0.5 ml of the test article applied to each foot covering the web spaces of both feet as well as the plantar and lateral aspect of both feet as well as on and around all toes and toe nails. The three test articles will be 10^6 CFUs/ml, 10^7 CFUs/ml, and 10^8 CFUs/ml. Each of the three groups will have 4 subjects. After the first cohort has completed their day 7 visits and if no significant tolerability of safety issues is identified the second cohort will be enrolled. After the second cohort has completed the day 7 visits and if no significant tolerability or safety issues are identified the third cohort will be enrolled.

Evaluations will be followed according to Table 2 Schedule of Events for Subjects. At all evaluations, signs and symptoms of application site reactions (local tolerability at sites unaffected by *T.pedis* interdigital) will be recorded. At baseline, days 2, 3 (+1), 7 (+/-1), 14 (+/-2), and 28 (+/-2), the signs and symptoms of *T. pedis* will be recorded. The investigators static global assessment (ISGA) of the interdigital *T. pedis* will be recorded at baseline, days 2, 3(+1), 7 (+/-1), 14 (+/-2), and 28 (+/-2). Subjects will also be queried for adverse events during their follow up visits or by self-reporting while on study until Day 28.

4.2 Study Endpoints

4.2.1 Primary Endpoints

a. Safety

- Tolerability will be evaluated through assessment of selected local signs and symptoms (pain / burning / stinging, pruritus, erythema, edema, and scabbing / crusting). Any local skin reaction that requires use of a concomitant therapy or study discontinuation should be reported as an AE on the Case Report Forms.

4.2.2 Secondary Endpoints

a. Efficacy

- Proportion of samples at each time point in which [REDACTED] can be detected by molecular diagnosis
- Proportion of samples at each time point in which *T. rubrum* can be detected by molecular diagnosis
- Relative abundance of *T. rubrum* at each time point
- Change in abundance of *T. rubrum*
- Changes in the signs and symptoms of *T. pedis*
- Change from dermatophyte culture positive to culture negative
- Change from KOH positive to KOH negative

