7. Classification toe web space. As not all web spaces are equally affected and the act of collecting samples from a web space could affect the laboratory results. Web spaces on both feet will be classified based on the ISGA at clear, almost clear, mild T. pedis, moderate T. pedis, severe T. pedis. In addition, one representative web space classified as moderate will be designated as the target sampling web space.
8. Signs and symptoms of local tolerability of the areas other than the web spaces.
9. Collect sample for reference mycology laboratory from the target sampling web space
10. Collect an e-swab from the target sampling web space.
11. Obtain digital photograph of the target sampling web space.
12. Assigned test article will then be applied to both feet. Approximately 0.5 ml of the test article will be applied to each foot spreading the test article over all web spaces, on and around all toe nails, the entire plantar and lateral aspects of the foot

13. One hour after application of the test article, the following activities will be done:

- a. E-Swab from an affected web space other than target sampling web space.
- b. Signs and symptoms of local tolerability of the areas other than the web spaces
- c. Record adverse event, if any.
- d. Given an appointment for Day 2 visit.

Detailed instruction for sample collection and processing are in the Study Operation Manual, provided separately.

Day 2 Approximately 24 hours after the test article was applied:

1. Concomitant medications.
2. Adverse events.
3. T. pedis ISGA of each web space on both feet.
4. T. pedis signs and symptoms.
5. Signs and symptoms of local tolerability of the areas other than the web spaces.
6. Collect an e-swab from an affected but previously not sampled web space. If none available collect e-swab from an unaffected but previously not sampled web space.
7. Give subject appointment for Day 3 visit.

Detailed instruction for sample collection and processing are in the Study Operation Manual, provided separately.

Day 3 Approximately 48 hours after the test article was applied:

1. Concomitant medications.
2. Adverse events.
3. T. pedis ISGA of each web space on both feet.
4. T. pedis signs and symptoms.
5. Signs and symptoms of local tolerability of the areas other than the web spaces.
6. Collect an e-swab from an affected but previously not sampled web space. If none available collect e-swab from an unaffected but previously not sampled web space.

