6.6.4 Sample Collection

One representative web space, according to the grading of signs and symptoms of *T. pedis*, must be classified as at least moderate to be designated as the Target Sampling (or target lesion) web space.

Subjects who have both feet affected, will have samples collected from each foot separately. Subjects that have one foot affected and the other foot unaffected, sample will only be collected from the affected foot. Indicate on the CRF if samples were collected from Left and/or Right foot.

For Microbial Sampling

If one foot is moderate and the contralateral foot is less than moderate the less than moderate foot will also be sampled.

For Drug Product Application

Both feet are treated even if one foot is not affected

Baseline Web space ISGA Grading	Microbial Sampling	Drug Product Application
Clear	No	Yes
Almost Clear	Yes, if contralateral is moderate	Yes
Mild	Yes, if contralateral is moderate	Yes
Moderate	Yes	Yes
Severe	Yes	Yes

Detailed instruction for sample collection and processing are in Table 3 below.

Table 3 Microbiological Samples

	Onsite KOH	Routine Mycology (Fungal Culture & KOH At Central Lab)	Molecular Diagnostics (e-swab)
Day 1 (Baseline -Prior to dose)	Target Sampling Web space	Target Sampling Web space	Target Sampling Web space
1hour after dose			Affected Web space other than Target Sampling Web space
Day 2			Previously not sampled affected Sampling Web space. If not available, then previously not sampled unaffected space.
Day 3			Previously not sampled affected Sampling Web space. If not available, then previously not sampled unaffected space.
Day 7		Target Sampling Web space	Target Sampling Web space
Day 14			Target Sampling Web space
Day 28		Target Sampling Web space	Target Sampling Web space

Throughout the study, continuous monitoring of concomitant medications, therapies and AEs will occur.

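### The two detection endpoints count samples, but section 6.6.4 takes two samples from some men and one from others; the plan needs one sampling rule and a per-man summary

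*Combined protocol and SAP*

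**What the plan says.** Section 4.2.2 and the efficacy part of the synopsis list four molecular endpoints. Two are detection endpoints expressed per sample: one for the product organism and one for the fungus, the latter worded "Proportion of samples at each time point in which *T. rubrum* can be detected by molecular diagnosis". The other two, the level ("Relative abundance of *T. rubrum* at each time point") and the change in abundance, are not proportions, and no unit is stated for them.

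How many samples a man gives depends on which part of the protocol is read.

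- **Section 6.6.4, text:** "Subjects who have both feet affected, will have samples collected from each foot separately". For one-sided disease: "Subjects that have one foot affected and the other foot unaffected, sample will only be collected from the affected foot". For unequal feet: "If one foot is moderate and the contralateral foot is less than moderate the less than moderate foot will also be sampled". The grid in the same section excludes a web space graded clear. The foot is to be recorded: "Indicate on the CRF if samples were collected from Left and/or Right foot".
- **Section 6.5.2:** at baseline "one representative web space classified as moderate will be designated as the target sampling web space". Each later visit list asks for one e-swab.
- **Table 3:** one sampling location per time point. This is the target web space at baseline and Days 7, 14 and 28, and a different web space at 1 hour, Day 2 and Day 3.

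Sections 6.11 to 6.14 plan descriptive presentation only, include all treated subjects, and give no rule for reducing two feet to one man.

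**The concern.** A proportion of samples equals a proportion of men only if every man gives the same number of samples. Under 6.6.4 he does not: the number depends on whether his disease is on one foot or both. Men sampled on both feet then enter the numerator and denominator twice, and the second sample may come from a milder foot.

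Descriptive percentages are the only summary this study will give of persistence of the organism and detection of *T. rubrum*. With four men per cohort, the mix of one-sided and two-sided disease can differ between cohorts by chance. A reader who sets the three dose levels side by side could take a difference in that mix for a difference due to dose.

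**Working it through.** **The plan's own figure.** Three cohorts of 4 give 3 × 4 = 12 men, as the synopsis states. Section 6.14 makes no sample-size assumptions, so there is nothing further to reproduce.

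**Inputs.** n = 4 men per cohort (synopsis, 4.1). Samples per man per time point: 2 if both feet are sampled, 1 otherwise (6.6.4). The number of men sampled on both feet, b, is not in the documents, so the full range 0 to 4 is shown.

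**Weights.** A cohort gives 4 + b samples. A man sampled on both feet carries weight 2/(4 + b) and a man sampled on one foot 1/(4 + b). Per man, each would carry 1/4.

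**Largest upward shift.** Suppose a man's two feet agree, all bilateral men are positive and all others negative. The sample proportion is 2b/(4 + b), the per-man proportion is b/4, and the shift is the difference.

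| b | Weight, two feet | Weight, one foot | Per sample | Per man | Shift (points) |
|---|---|---|---|---|---|
| 0 | none | 25% | 0/4 = 0% | 0/4 = 0% | 0 |
| 1 | 40% | 20% | 2/5 = 40% | 1/4 = 25% | +15 |
| 2 | 33% | 17% | 4/6 = 67% | 2/4 = 50% | +17 |
| 3 | 29% | 14% | 6/7 = 86% | 3/4 = 75% | +11 |
| 4 | 25% | none | 8/8 = 100% | 4/4 = 100% | 0 |

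**Largest downward shift.** Reverse the pattern, so that bilateral men are negative and the others positive. The proportions are (4 − b)/(4 + b) per sample and (4 − b)/4 per man:

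- b = 1: 3/5 = 60% against 3/4 = 75%, −15 points
- b = 2: 2/6 = 33% against 2/4 = 50%, −17 points
- b = 3: 1/7 = 14% against 1/4 = 25%, −11 points

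**All 12 men pooled.** The largest shift is at b = 5: 10/17 = 59% against 5/12 = 42%, or 17 points. It is zero at b = 0 and b = 12.

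**When a man's feet disagree.** Equal weights do not remove the need for a rule. If all four men are sampled on both feet and each has one positive foot, the result is 4/8 = 50% of samples but 4/4 = 100% of men under an any-foot-positive rule.

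**The other reading.** If 6.5.2 and Table 3 govern, each man gives one e-swab per time point, 4 men give 4 samples, and the two proportions are identical.

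**The case against.** The strongest reply is that the double count is conditional. The visit lists and Table 3 imply one swab per man, and sampling detail is deferred to a Study Operation Manual that is not among the documents. This stands: the contradiction in sampling comes first, and the weighting problem follows only if 6.6.4 governs. It does not dispose of the point, because 6.6.4 explicitly calls for samples from each foot and a site cannot tell from the protocol which passage applies.

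A second reply is that everything is descriptive, the data will be listed and the foot is recorded. The synopsis even names a data listing of detection time as a criterion for persistence. So per-man results can be recovered. That limits the harm, but the endpoint as defined would still be tabulated per sample.

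A third reply is that the shifts are worst cases and smaller than the 25 points by which one man moves a per-man percentage in a cohort of four. Both statements are true. The sample-weighting shift comes on top of that coarseness and is avoidable.

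A reader might also infer that the unit of analysis is wrong, that the plan treats two feet as independent, or that its precision is overstated. The documents do not support this. No standard error, interval or test is specified, and a clearly labelled per-sample proportion is a legitimate description, particularly as product is applied to each foot.

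**Conclusion.** The point holds for the two detection endpoints, conditionally on 6.6.4 governing the sampling. In a cohort of four with one to three men sampled on both feet, the reported percentage can then depart from the per-man percentage by up to about 11 to 17 points either way. Those figures assume the number of bilateral men, agreement between a man's two feet, and the most extreme split between bilateral and unilateral men. They are bounds, not expected values. If b is 0 or 4 the weights are equal.

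The point does not extend to all the molecular endpoints. Relative abundance and change in abundance are not sample proportions, although their unit should also be stated. Nor does it touch escalation, which rests on the Day 7 safety review in section 7.1. It is a correction worth making to secondary endpoints.

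**What to change.** 1. Reconcile 6.6.4 with 6.5.2 and Table 3 so that the number of e-swabs per man at each time point, and the foot each comes from, is stated once.
2. In the synopsis and 4.2.2, change the two detection endpoints to the proportion of subjects at each time point. Fix in advance one rule for men with two sampled feet that works at every visit: for example, one foot designated at baseline, the foot containing the target web space, or any foot positive.
3. Present foot-level results separately in listings, using the left/right entry on the CRF.

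The endpoint should not be tied to the single target web space. Table 3 takes the swab elsewhere at 1 hour, Day 2 and Day 3, so such an endpoint would have no data at three of the seven swab time points.

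**Cost.** Protocol wording and table shells; the per-man summary can be built from samples already planned. Each cohort percentage then has a denominator of 4 and moves in steps of 25 points. If a one-foot rule is chosen, the second foot appears only in listings.
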